Merck Investigator Studies Program (MISP) Protocol

Fall in prevalence of genital HPV infection in males following introduction of universal male HPV vaccination

Section 1: MISP Protocol Identification

Principle Investigator

Associate [name]*

Institution name:

University of Melbourne and Melbourne Sexual Health Centre

Co-Investigators

[name]

University of Melbourne and Melbourne Sexual Health Centre

Associate [name]

University of Melbourne and Melbourne Sexual Health Centre

[name]

University of New South Wales

Associate [name],

University of Melbourne and Royal Women's Hospital

[name]

University of Melbourne and Royal Women's Hospital

Associate [name]

University of Melbourne

[name]

University of New South Wales

[name]

National HPV Vaccination Program Register

Associate [name]

Sydney Sexual Health Centre

Associate [name]

[name] RPA Sexual Health

[name]

Western Sydney Sexual Health Service

Associate [name]
Cairns Sexual Health Service

[name]
Clinic 275, Royal Adelaide Hospital

[name]
Department of Infectious Diseases, Freemantle

[name],
Tasmania State wide Sexual Health Service

*Principle Investigator contact details:

[name]
Melbourne Sexual Health Centre,
[name].
[contact]. [contact]
Email: [contact]

Current version: 4, 21st April 2015

Section 2

2.1: Objective and hypothesis

The aim of this study is to demonstrate a fall in the prevalence of genital HPV infection among teenage males as a result of the implementation of a universal male vaccination program. Our hypothesis is that in a setting where there is already a female vaccination program in place and where herd immunity has resulted in a fall in male HPV prevalence, introduction of a male vaccination program will result in further falls in the prevalence of HPV in males.

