2.2 Background

Rationale for study

The provision of HPV vaccination to females through universal vaccination programs has resulted in a fall in prevalence of HPV infection and HPV related lesions among females in countries where this has been introduced. This has been shown in several countries including Australia, which was one of the first countries to roll out free, universal vaccination in females. In Australia studies have shown a significant decline in the prevalence of HPV infection, genital warts and HPV related cervical lesions among females.¹⁻⁴

While such direct benefits have been shown in females, they have not been shown among males as no country to date has rolled out universal, free vaccination of males on a national level. Rather, what has been shown to date are falls in the prevalence of genital warts as a result of herd immunity from female vaccination.¹⁻² Mathematical models predict that extending the vaccination program to males will provide incremental benefit.⁵ While this is predicted to occur, there have to date been no data from any countries demonstrating this as no countries have thus far implemented universal vaccination of both males and females.

As the Australian Government has announced that a universal male vaccination program will be introduced in Australia beginning in 2013 we believe we are uniquely placed in Australia to document a fall in HPV prevalence among males that is additional to falls that have already occurred because of female vaccination.

If this study is to be undertaken it is critical that it begins as soon as possible given that vaccination is being rolled out in Australia in 2013. Without this we cannot establish the baseline prevalence of HPV among males prior to male vaccination.

In Victoria the male vaccination program will be provided through:

- An ongoing school based program to boys in year 7 (mainly 12 and 13 year olds with some 11 year olds) with a time limited program for boys in year 9 (mainly 14 and 15 year olds with some 13 year olds) in 2013 and 2014 only.
- An ongoing community based program for boys aged 12 and 13 years together with a time limited program for boys aged 14 and 15 in 2013 and 2014 only.

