This means that by 2014, 2015, 2016 and 2017, the oldest cohort of males to have been offered vaccination as part of the Victorian program will be aged 16, 17, 18 and 19 years respectively. The age of boys who will have been offered vaccination by year from 2013 through to 2017 is shown in Table 1. In period 1 (2014-2015), 200 boys will be recruited. The same number, 200, will be recruited in period 2 (2016-2017).

Significance of study outcomes

As Australia is the first country to implement a universal male vaccination program we have the opportunity to be among the first to demonstrate a fall in HPV prevalence among males as a result of male vaccination. While there is

evidence that the prevalence of genital warts among males in Australia has fallen as a result of female only vaccination, falls in the prevalence of HPV infection including high risk HPV types among males in response to universal male vaccination have not thus far been documented in any country but is expected to occur.⁵

[figure not shown]
This would provide evidence and argue for the introduction of universal male HPV vaccination programs in countries which have already introduced universal vaccination of females.

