2.7 Statistical analysis

The primary outcome of interest will be the change in prevalence of quadrivalent vaccine types (6, 11, 16 and 18) among 17-19 year old men in the two time periods. The study will also provide data on the change in prevalence of non-vaccine types.

The required sample size for each year is dependent upon the expected prevalence of genital HPV and affects the precision of the prevalence estimates (95% confidence intervals, CI) in the two cross sectional samples. Different prevalence rates and 95%CI are shown for various sample sizes in Table 1.

Table 1: Estimated 95% confidence intervals for differing HPV prevalent rates and sample sizes

HPV prevalence rate (%)	Sample size (persons)				
	100	200	300	400	500
5	0.0186-0.1183	0.0256-0.0927	0.0293-0.0829	0.0316-0.0774	0.0333-0.0739
10	0.0516-0.1804	0.0637-0.1523	0.0695-0.1411	0.0732-0.1347	0.0758-0.1305

Previous estimates of HPV infection have been determined by investigators in our group for females but are not available for males.⁴ A sample size of 200 males in each of the two periods would provide reasonable confidence intervals around expected prevalence rates for individual HPV types. This would require a total of 400 males for the entire four year study.

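### The aim credits the male programme with any fall, but section 2.7 plans only a crude two-period change, which supports that attribution weakly

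*Combined protocol and SAP*

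**What the plan says.** The aim in section 2.1 is a fall "among teenage males as a result of the implementation of a universal male vaccination program", and the hypothesis predicts further falls beyond those from female vaccination. Section 2.2 speaks of "a fall in HPV prevalence among males that is additional to falls that have already occurred because of female vaccination". Under its heading on the significance of study outcomes it hopes to "demonstrate a fall in HPV prevalence among males as a result of male vaccination", and says that the result would provide "evidence and argue for the introduction of universal male HPV vaccination programs" in countries that already vaccinate females. The title is neutral: "Fall in prevalence of genital HPV infection in males following introduction of universal male HPV vaccination".

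Section 2.7 is the whole statistical plan. It says: "The primary outcome of interest will be the change in prevalence of quadrivalent vaccine types (6, 11, 16 and 18"), compared between the two periods in men aged 17-19. It adds: "The study will also provide data on the change in prevalence of non-vaccine types". It names no effect measure, test, model, adjustment or contrast between type groups.

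Section 2.3 treats period 1 (2014-2015) as a baseline that already carries the female herd effect. Section 2.5 recruits through universities, sexual health services and advertising, without fixing the mix by period. It collects sexual and vaccination histories, but section 2.7 uses neither.

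**The concern.** A before-and-after difference between two independent samples can have several causes. Three are left open here:

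- The balance between service attendees and university or advertising recruits may differ between periods.
- Behaviour or sampling may change in a way that moves all HPV types.
- The herd effect of female vaccination may keep growing after period 1, on the same four types.

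The first two could be examined with genotypes and questionnaire items already collected, plus a record of recruitment source. The plan does not say that they will be. If the role of the non-vaccine types is settled only after the data are seen, its reading is discretionary. The result is meant to inform male vaccination policy elsewhere, so a fall from another cause read as a programme effect would matter.

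**Working it through.** **1. The plan's own figure.** The only quantitative basis for 200 per period is the interval table in section 2.7. It is reproduced by the Wilson interval with continuity correction. At p = 0.05, n = 200, z = 1.96:

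- Lower = [2np + z² − 1 − z√(z² − 2 − 1/n + 4p(n(1−p)+1))] / [2(n+z²)] = (20 + 3.84 − 1 − 12.40)/407.7 = 0.0256.
- Upper = [2np + z² + 1 + z√(z² + 2 − 1/n + 4p(n(1−p)−1))] / [2(n+z²)] = (20 + 3.84 + 1 + 12.95)/407.7 = 0.0927.

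Both match. At 10% the result is 0.0637-0.1523, also a match. These intervals describe one prevalence in one period. They do not address the change or its cause.

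**2. What the design does provide.** By the Victorian ages in section 2.2, the oldest males offered vaccine are 16, 17, 18 and 19 in 2014 to 2017. Counting age-by-year cells for ages 17-19:

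- Period 1: only age 17 in 2015, so 1 of 6.
- Period 2: ages 17 and 18 in 2016, and 17, 18 and 19 in 2017, so 5 of 6.

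The contrast in exposure is real. These are cells and not men, they show offer and not uptake, and they are for Victoria only, while section 2.5 seeks ethics approval in several states.

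**3. Recruitment mix, no vaccine effect.** Section 2.7 says that prior estimates were "determined by investigators in our group for females but are not available for males", so all rates here are assumptions: 20% in service recruits, 5% in others. Prevalence = share × 20% + (1 − share) × 5%. PR is the prevalence ratio, period 2 over period 1.

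| Service share | Period 1 → 2 prevalence | Spurious PR | Rejection, unadjusted | Rejection, stratified by source |
|---|---|---|---|---|
| 50% → 50% | 12.5% → 12.5% | 1.00 | 4.4% | 4.2% |
| 50% → 40% | 12.5% → 11% | 0.88 | 6.6% | 4.8% |
| 50% → 25% | 12.5% → 8.75% | 0.70 | 21.5% | 4.0% |

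Rejection rates are for a two-sided 5% test in 3,000 simulated studies of 200 per period, with a Mantel-Haenszel PR for the stratified test. A share rising to 60% gives 14%, so PR 1.12, which would mask a fall.

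**4. What a comparator adds.** Let vaccine types fall from 10% to 5% (PR 0.50). With outcomes treated as independent, if non-vaccine types stay at 20% the ratio of PRs is 0.50 (95% CI 0.22-1.15). If they halve to 10% it is 1.00 (0.41-2.43). The primary outcome is the same in both cases.

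The control is partial. At 50% → 25%, assume non-vaccine prevalence of 30% in service recruits and 15% in others. It falls from 22.5% to 18.75%, PR 0.833, so the ratio is 0.70/0.833 = 0.84 despite no effect. A Poisson model fitted to these expected values with one shared source term still gives 0.84. Letting the source effect differ by type group gives 1.00.

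**5. Precision, 10% to 5%, 200 per period.**

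- SE(log PR) = √(0.9/20 + 0.95/10) = √0.14 = 0.374. The 95% CI is 0.24-1.04. Power = Φ(0.693/0.374 − 1.96) = 46%.
- The ratio of PRs adds the non-vaccine variances and, because both outcomes come from the same men, subtracts 2ρ√(v(1−v)w(1−w))/(200vw) per period, where v and w are the vaccine and non-vaccine prevalences.
- Constant w of 10%, ρ = 0: variance 0.14 + 0.09 = 0.23, CI 0.20-1.28, power 30%.
- Constant w of 30%, ρ = 0.3: variance 0.14 + 0.0233 − 2 × 0.0169 = 0.130, CI 0.25-1.01, power 49%.

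**6. Vaccination history.** Even at 100 against 100 men and 10% against 5%, SE = √(0.9/10 + 0.95/5) = 0.529 and the CI is 0.18-1.41.

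**The case against.** The strongest reply is that the design already supports attribution in part. The periods are timed to the rollout. Age range, residence from age 12 and the exclusion of recent sex with men are the same in both. Non-vaccine change is reported, so a general fall would be visible. The title is neutral and section 2.7 promises only a change, so the causal phrases are statements of aim. The quantified bias rests on invented prevalences and shares, nothing in the protocol predicts a changing mix, and a moderate shift does little harm. A formal ratio of PRs costs power that is already low.

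Much of this stands. A reader might infer that the study cannot support attribution at all. The documents do not bear that out: 1 of 6 against 5 of 6 cells offered vaccine, together with the non-vaccine types, is evidence, though weak. A reader might also infer that only rewording can respond to the female herd effect. That is too strong. Vaccinated and unvaccinated men within a period share much of the same female background, and their vaccination history is collected. The contrast is sparse, confounded by uptake and silent on indirect effects, but it is not empty.

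What does not stand is leaving the analysis unspecified. Reporting the non-vaccine types without saying how they bear on the conclusion is not a safeguard, and low power does not justify causal wording.

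**Conclusion.** The point holds as a mismatch between a causal aim and a crude two-period analysis. Support for attribution is weak, and three rival explanations are not guarded against.

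The size of a continuing female herd effect cannot be derived from the documents, so none is given. Non-vaccine types would not reveal it if it is confined to the four vaccine types. The recruitment-mix figures show what is possible, not what is likely. False rejection reaches about 20% only if the service share halves under assumed prevalences of 20% and 5%, and is about 6.5% for a fall to 40%. It would be wrong to read them as showing that the primary result will be biased, or to read the negative control as rescuing a causal claim.

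**What to change.** A cheap improvement, in wording and analysis only:

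1. In section 2.1 and in the significance paragraphs of section 2.2, replace *as a result of* with *following*, as in the title. Reword the hypothesis, which predicts that the programme will bring further falls, to match. State that the two-period change does not by itself separate the male programme from a continuing female herd effect on the same four types.
2. In section 2.7, report the period 2 to period 1 PR for any of types 6, 11, 16 and 18 with a 95% CI, unadjusted and adjusted for recruitment source, age and number of partners. Enter source first if positives are few: 10% to 5% gives 20 + 10 = 30 in all, and 5% to 2.5% gives 10 + 5 = 15.
3. Name any of the other 33 genotypes (37 − 4, from the list in section 2.5) as a partial negative-control outcome, and report its PR beside the vaccine-type PR. Give the ratio of PRs as a secondary estimate with no pass/fail rule. Its CI should allow for both outcomes coming from the same men, and the source effect should be free to differ by type group where the data permit.
4. Report prevalence of the four types by self-reported vaccination history within period, as supportive and descriptive only, with the limits noted above.

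No extra men, visits or assays are needed. Source can be recorded when the kit is handed out or posted. The costs are statistical: wide intervals at 200 per period, a possible loss of up to about a third of the power for the ratio of PRs (30% against 46%), and adjustment that covers only the measured mix.

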2.2 Background

Rationale for study

The provision of HPV vaccination to females through universal vaccination programs has resulted in a fall in prevalence of HPV infection and HPV related lesions among females in countries where this has been introduced. This has been shown in several countries including Australia, which was one of the first countries to roll out free, universal vaccination in females. In Australia studies have shown a significant decline in the prevalence of HPV infection, genital warts and HPV related cervical lesions among females.¹⁻⁴

While such direct benefits have been shown in females, they have not been shown among males as no country to date has rolled out universal, free vaccination of males on a national level. Rather, what has been shown to date are falls in the prevalence of genital warts as a result of herd immunity from female vaccination.¹⁻² Mathematical models predict that extending the vaccination program to males will provide incremental benefit.⁵ While this is predicted to occur, there have to date been no data from any countries demonstrating this as no countries have thus far implemented universal vaccination of both males and females.

As the Australian Government has announced that a universal male vaccination program will be introduced in Australia beginning in 2013 we believe we are uniquely placed in Australia to document a fall in HPV prevalence among males that is additional to falls that have already occurred because of female vaccination.

If this study is to be undertaken it is critical that it begins as soon as possible given that vaccination is being rolled out in Australia in 2013. Without this we cannot establish the baseline prevalence of HPV among males prior to male vaccination.

In Victoria the male vaccination program will be provided through:

- An ongoing school based program to boys in year 7 (mainly 12 and 13 year olds with some 11 year olds) with a time limited program for boys in year 9 (mainly 14 and 15 year olds with some 13 year olds) in 2013 and 2014 only.
- An ongoing community based program for boys aged 12 and 13 years together with a time limited program for boys aged 14 and 15 in 2013 and 2014 only.

This means that by 2014, 2015, 2016 and 2017, the oldest cohort of males to have been offered vaccination as part of the Victorian program will be aged 16, 17, 18 and 19 years respectively. The age of boys who will have been offered vaccination by year from 2013 through to 2017 is shown in Table 1. In period 1 (2014-2015), 200 boys will be recruited. The same number, 200, will be recruited in period 2 (2016-2017).

Significance of study outcomes

As Australia is the first country to implement a universal male vaccination program we have the opportunity to be among the first to demonstrate a fall in HPV prevalence among males as a result of male vaccination. While there is

evidence that the prevalence of genital warts among males in Australia has fallen as a result of female only vaccination, falls in the prevalence of HPV infection including high risk HPV types among males in response to universal male vaccination have not thus far been documented in any country but is expected to occur.⁵

[figure not shown]
This would provide evidence and argue for the introduction of universal male HPV vaccination programs in countries which have already introduced universal vaccination of females.

2.3 Study design

Study population and sample size

This study will determine the prevalence of genital HPV among males aged 17-19 years using two cross sectional samples, the first obtained over 2014-2015 (period 1) and the second over 2016-2017 (period 2) (Table 1). Given the differing age groups that will have been offered vaccination over the four years, period 1 will provide baseline prevalence among males prior to the vaccination program – a prevalence that reflects herd immunity from pre-existing vaccination of females. In period 1, most 17-19 year old males will not have been offered the vaccine (Table 1). By contrast, in period 2, most 17-19 year old males will have been offered vaccination as part of the male vaccination program (Table 1).

2.4 Study flowchart

2.5 Study procedures

This study will recruit 17 to 19 year old males from universities and other sources including sexual health services. Potential participants will be identified by a nurse or doctor if they present to a health service or if they become aware of the study through advertising will discuss the study with a research nurse.

Eligibility criteria

- Male
- Aged 17 to 19*
- Residing in Australia from 12 years of age[#]
- Able to complete study requirements

Exclusion criteria

- Males who report sex with men in the past 12 months

*Must be aged 17, 18 or 19 years during the four year study period, that is, January 1 2014 through to December 30 2017.

[#]This is to ensure that males included in the study were present in Australia at the time HPV vaccination was offered.

Men who agree to the study will be asked to provide informed, written consent and undertake self-testing for genital HPV and a questionnaire will be obtained. Self-collection of the swab will be completed at the participants convenience using postal specimens that include a self-testing kit that is either given to participants attending services or posted out if recruitment is via advertising.

The questionnaire will capture:

- Demographic information such as age and education level.
- Detailed sexual history including: age at first sex; number and gender of sexual partners over different time periods; sexual practices including oral, anal and vaginal sex; and condom use.
- Relevant medical information such as history of genital warts, circumcision status, and smoking.

- History of previous HPV vaccination

HPV DNA sampling

Each man in the study will be asked to obtain a genital specimen which will be self-collected by participants using a swab on the glans penis, coronal sulcus, foreskin (if uncircumcised), and penis.

Laboratory testing for HPV DNA

Samples will be tested at the Regional HPV Labnet Reference Laboratory, Molecular Microbiology Department, Royal Women's Hospital, Melbourne. Cellular material will be pelleted in 1mL aliquots by centrifugation at 5,000 ×g and resuspended in 200 µL PBS. Total DNA will be extracted on the MagNA Pure 96 using the MagNA Pure 96 DNA and Viral NA small volume kit (Roche Diagnostics GmbH, Penzberg, Germany).

Extracted DNA will be pre-screened to assess its integrity by quantitative PCR amplification of a 260 base pair product of the human beta-globin gene.⁶

Samples will subsequently be amplified for HPV L1 gene using consensus primers PGMY09-PGMY11⁷ and amplicons detected using the PCR ELISA System (Roche Diagnostics GmbH, Penzberg, Germany). A generic probe for detection of the presence of any HPV sequences in the sample using biotin-labelled probes will be used to detect all mucosal HPV types. Samples that are positive by ELISA will be further genotyped by HPV Linear Array genotyping assay (Roche Molecular Systems, Pleasanton, California), involving PCR amplification of target DNA followed by nucleic acid hybridization and detection of 37 HPV genotypes (6, 11, 16, 18, 26, 31, 33, 35, 39, 40, 42, 45, 51, 52, 53, 54, 55, 56, 58, 59, 61, 62, 64, 66, 67, 68, 69, 70, 71, 72, 73, 81, 82, 83, 84, 82v and 89).

Ethical approval

Ethical approval for this study will be obtained from each state in which recruitment is intended to occur. A NEAF will be submitted to the Alfred Hospital Research Ethics Committee, South Eastern Sydney Local Health District ethics committee, Far North Queensland Human Research Ethics Committee, Royal Adelaide Hospital Committee, Tasmania Health and Medical Human Research Ethics Committee and South Metropolitan Health Service Human Research Ethics Committee. Site Specific Applications will be made for each site once NEAF approval has been given.

Men will not routinely be informed of their HPV results as HPV testing is not standard clinical practice, HPV is mostly self-limiting, does not cause symptoms and has no treatment if asymptomatic. Accordingly, routine provision of results would be likely to induce more stress among participants that is warranted.

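### Clinic recruitment neither restricts nor records the reason for attendance, so a shift between periods in the share of men attending for genital warts could distort the absolute change in vaccine-type prevalence

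*Combined protocol and SAP*

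**What the plan says.** Section 2.5 gives the sources: "This study will recruit 17 to 19 year old males from universities and other sources including sexual health services". For clinics it adds: "Potential participants will be identified by a nurse or doctor if they present to a health service". The single exclusion is sex with men in the past 12 months. No criterion mentions warts, symptoms or reason for presenting. The questionnaire includes a history of genital warts, but the listed items do not include why a man attended. No source mix is fixed for either period. The feasibility text in section 2.6 mentions a network of clinical sites without saying what share of the sample they will supply.

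Section 2.7 names the primary outcome as "the change in prevalence of quadrivalent vaccine types (6, 11, 16 and 18) among 17-19 year old men", compared between the two periods. It does not say whether the change is absolute or relative, and it plans no restriction, stratification or sensitivity analysis by source or wart status.

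On warts, the significance text in section 2.2 refers to "evidence that the prevalence of genital warts among males in Australia has fallen as a result of female only vaccination".

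**The concern.** A man who goes to a clinic because of warts enters the sample as a result of an HPV infection, usually with type 6 or 11. Those are two of the four types in the primary outcome. For these men sampling depends on what is being measured, and the observed prevalence in each period depends partly on how many of them were enrolled.

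The aim is to show a further fall due to male vaccination, beyond that from female vaccination. The share of wart attenders could move between periods for unrelated reasons, such as a shift between clinic and university recruitment or a change in referral patterns. That movement would then be counted as programme effect, or would conceal it.

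Stratifying by clinic versus university would handle a change in source mix but not a change in why men attend within clinics. The planned data on non-vaccine types would not expose the problem either, because selection through warts acts mainly on types 6 and 11.

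**Working it through.** **The plan's own figures.** The interval table in section 2.7 gives, at 200 men, 0.0256-0.0927 for 5% prevalence and 0.0637-0.1523 for 10%. A Wilson score interval with continuity correction reproduces all ten cells to four decimals. The total is 2 × 200 = 400. These intervals describe sampling error only.

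**Inputs.** From section 2.7: n = 200 per period, and background prevalence p0 of 5% or 10%, the two planning rates. Assumed, because the documents do not give them: w, the share of the whole sample attending because of warts, and q, vaccine-type positivity in those men, taken as 50% to 90%.

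**Formula.** Observed prevalence = w·q + (1 − w)·p0. With no true change in other men, the spurious fall = (w1 − w2)·(q − p0). The factor q − p0 runs from 0.50 − 0.10 = 0.40 to 0.90 − 0.05 = 0.85.

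| Wart share, period 1 to 2 | Men of 200 | Smallest spurious fall | Largest spurious fall | Prevalence ratio |
|---|---|---|---|---|
| 2% to 1% | 4 to 2 | 0.01 × 0.40 = 0.4 points | 0.01 × 0.85 = 0.85 points | 0.96 to 0.87 |
| 5% to 2.5% | 10 to 5 | 0.025 × 0.40 = 1.0 points | 0.025 × 0.85 = 2.1 points | 0.92 to 0.77 |
| 10% to 5% | 20 to 10 | 0.05 × 0.40 = 2.0 points | 0.05 × 0.85 = 4.25 points | 0.86 to 0.69 |

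One cell in full: with q = 70% and p0 = 5%, period 1 is 0.10 × 0.70 + 0.90 × 0.05 = 11.5% and period 2 is 0.05 × 0.70 + 0.95 × 0.05 = 8.25%. That is a fall of 3.25 points and a ratio of 0.72.

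**Direction.** If the share rises from 5% to 10%, the signs reverse and observed prevalence goes up by 2.0 to 4.25 points.

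**What the shares mean.** w is the clinic share of the sample times the wart share among clinic recruits. Half from clinics with 10% of those attending for warts gives w = 5%, or 10 men of 200. A quarter from clinics with 10% gives 2.5%, or 5 men.

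**When background prevalence falls in proportion.** Let p0 go from 10% to 5% and w from 5% to 2.5%. With q = 70%, period 1 is 0.035 + 0.095 = 13.0% and period 2 is 0.0175 + 0.04875 = 6.625%. The absolute fall is 6.4 points against a true 5.0, but the ratio is 0.51 against 0.50. With q = 100%, the figures are 14.5% and 7.375%, a fall of 7.1 points and again a ratio of 0.51.

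**Scale.** The plan names no test. Under an assumed two-sided 5% test, 200 per period gives 80% power for 10% falling to about 3%, or 5% falling to about 0.5%.

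**The case against.** The strongest objection concerns the mechanism. The protocol says that warts have fallen, in the past tense, and treats herd immunity from female vaccination as already part of the period 1 baseline. Nothing says that wart attendance will keep falling into 2016-2017 without male vaccination. If herd immunity did continue, it would lower warts by lowering vaccine-type infection, so background prevalence would fall too. That is the ordinary secular-trend limitation of a before-after design, present with no wart patients at all, and in that case the prevalence ratio barely moves. This stands. A reader might infer from the background text that a spurious fall is to be expected; the documents do not support that. What remains is a shift in wart share from other causes, such as source mix or referral, in either direction.

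Second, the shares and positivity are all assumed. Universities are listed first among the sources, and section 2.6 expects no difficulty recruiting there, so the clinic share could be small. Swabs are self-collected, so detection may be incomplete. This also stands, and is why only a range can be given. Even in the 10% to 5% row the bias is about 0.6 to 1.3 standard errors of the difference (for 14% versus 12%, √(0.14 × 0.86/200 + 0.12 × 0.88/200) = 3.4 points; for 13.5% versus 9.25%, 3.2 points).

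Third, wart attenders are admitted by omission. The protocol does not say that they are sought, and the flowchart in section 2.4 is not visible in the text available for review. Wart history is collected, so some sensitivity analysis is possible already. But past warts do not show why a man attended, and section 2.7 plans no use of the item.

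Fourth, excluding wart attenders also conditions on a consequence of the outcome. If male vaccination reduces wart attendance, exclusion removes more positive men in period 1 than in period 2 and shrinks the true absolute fall. This argues against making exclusion the only primary analysis, but not against reporting both comparisons.

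**Conclusion.** The gap is real. Men can enter the sample because of the infection being measured, and the plan has no means of seeing how many did so or whether that number changed between periods. A decline in their share for reasons other than male vaccination overstates the absolute fall; a rise hides a true one.

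The size is unknown. It is under 1 point if wart attenders are about 2% of the sample or fewer, and 1.0 to 4.25 points if they start at 5% to 10% and halve. Those figures assume 50% to 90% positivity, background prevalence of 5% or 10%, and no true change in other men. Against planning prevalences of 5% and 10%, the upper part of that range matters.

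Two stronger readings go too far. One is that an observed fall would be an artefact of wart attendance: the documents give no shares from which to conclude that, and part of any decline in wart attendance may itself be an effect of male vaccination. The other is that the prevalence ratio is equally distorted: it is almost unaffected when background prevalence falls in proportion.

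**What to change.** - Add one item to the recruitment form for every clinic recruit in both periods: main reason for attendance, with genital warts or lumps as a category. Version 4 is dated within period 1, so for any man already enrolled without the item, say how it will be completed or counted as missing.
- Prespecify in section 2.7 the between-period comparison for all recruits and again excluding men who attended for warts.
- Report the number of such men and the recruitment source mix in each period.
- Report types 6/11 separately from 16/18. The Linear Array genotyping in section 2.5 already supplies this.

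The cost is one form item and a little more analysis. The restricted comparison drops a few men and may understate the absolute fall if male vaccination itself reduces wart attendance, so the two comparisons should be read together.
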